2.3 RISK/BENEFIT ASSESSMENT

2.3.1 KNOWN POTENTIAL RISKS

Elimination diets: Elimination diets may affect nutritional status, eating pleasure, and quality of life.²³ However, again, given that the study duration is 8 weeks, significant nutritional deficiencies are unlikely.

2.3.2 KNOWN POTENTIAL BENEFITS

Elimination Diets: Benefits include relative safety and potential long-term maintenance. Recent studies have demonstrated a response to elimination diets in 30-60% of EoE patients. However the effects of the FREE diet have not been evaluate in patients with EoE.

2.3.3 ASSESSMENT OF POTENTIAL RISKS AND BENEFITS

This is a pragmatic trial comparing two standard of care treatments for EoE. Therefore, the risks are no greater than those ordinarily encountered in daily life. Furthermore, there is the prospect of benefit to enrolled patients (e.g. symptom reduction and improved quality of life). The risks are considered low and the benefit to the overall group of patients with EoE would be considered significant.

3 OBJECTIVES AND ENDPOINTS

OBJECTIVES	ENDPOINTS	JUSTIFICATION FOR ENDPOINTS
Primary		
To compare histologic outcomes of DED and FREE among children with eosinophilic esophagitis	Maximum eos/hpf (primary)	Eosinophils are a biomarker of inflammation. Current diagnostic criteria specify ≥ 15 eos/hpf. A reduction in eos/hpf should correlate with a reduction in symptoms. A successful treatment outcome is < 15 eos/hpf.
Secondary		
To compare endoscopic outcomes of DED and FREE among children with eosinophilic esophagitis	Eosinophilic Esophagitis Endoscopic Reference Score (EREFs)(secondary)	Includes additional eosinophil morphology and associated histopathologic features (e.g. degranulation, microabscesses, superficial layering, basal zone hyperplasia)
Tertiary/Exploratory		
To compare quality of life and patient reported outcomes of DED and FREE among children with eosinophilic esophagitis	PedsQL-EoE (tertiary) Pediatric Eosinophilic Esophagitis Symptom Severity Module (PEESS) (tertiary)	Determines the impact of DED and FREE on QOL and symptom severity, which is not routinely assessed.

4 STUDY DESIGN

4.1 OVERALL DESIGN

Prospective, pragmatic standard of care clinical trial comparing dietary therapies of dairy elimination diet (DED) vs. dairy elimination and food additive elimination (FREE). After obtaining informed consent, participants will perform screening procedures. If all eligibility criteria are met, the patient will be randomized to one of the two diet regimens. Patients will receive dietary counseling at baseline. All participants will be followed via phone calls and REDCap surveys for the duration of the study.

4.2 SCIENTIFIC RATIONALE FOR STUDY DESIGN

Food elimination diets have resulted in remission in an estimated 30-60% of patients. Typically, a six-food elimination diet is successful, yet it is difficult to maintain long-term adherence. Because the majority of allergens are found in four of these six foods, a four-food elimination diet has been suggested and demonstrated 60% remission in children in one study. Furthermore, other studies shown up to a 50% response rate when eliminating dairy alone. The dairy free diet has not been directly compared to a dairy free plus additive free diet.

4.3 END OF STUDY DEFINITION

The end of the study will be the point at which all required data has been collected or the date of the last patient visit.

5 STUDY POPULATION

5.1 INCLUSION CRITERIA

Inclusion criteria

To be eligible to participate in this study, all of the following criteria must be met:

1. An Institutional Review Board (IRB) approved written Parental Permission form is signed and dated by the parent or legal representative/caregiver.
2. An Institutional Review Board (IRB) approved written Assent form is signed and dated by the participant.
3. The participant/parent(s) or legal representative(s)/caregiver(s) are considered reliable and capable of adhering to the protocol call schedule and dietary requirements.
4. The participant is ≥ 2 years to 18 years of age.
5. The participant has isolated esophageal eosinophilia (>15 eos/hpf).
6. The biopsy used to diagnose eosinophilic esophagitis was taken no more than 12 weeks prior to the date of enrollment.
7. The family has access to the internet to complete weekly surveys and to a telephone to complete weekly follow up calls.

5.2 EXCLUSION CRITERIA

1. The participant has peripheral eosinophilia $> 1,500 \mu\text{L}$
2. The participant has concomitant GI inflammatory conditions (e.g. celiac disease, inflammatory bowel disease).
3. The participant has a history of upper GI tract surgery (e.g. fundoplication)

4. Acid reflux by pH probe is suggested (*A pH probe is not required, but may be done as standard of care)
5. The participant has severe developmental delay that, in the opinion of the investigator, could jeopardize the participant's ability to participate in the study.
6. The participant has taken prednisone in the last 12 weeks, or has taken fluticasone or budesonide in the last 8 weeks
7. The participant has other significant medical conditions that, in the opinion of the provider, would impact the participant's ability to participate in the study.
8. The participant has a psychiatric condition that, in the opinion of the investigator, could jeopardize the participant's ability to participate in the study.
9. The participant does not speak or read English fluently.
10. The participant is currently taking a PPI (If discontinued, no washout is required.)
11. The participant is currently on or has previously failed dairy elimination therapy.

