A Food Additive Removal Diet for Pediatric Eosinophilic Esophagitis (FREE)

Principal Investigator: [name]

Funded by: Anonymous Donor to the Nemours Foundation

Version Number: v.13

22JUL2020

Summary of Changes from Previous Version:

Affected Section(s)	Summary of Revisions Made	Rationale
1-9	
v.2
 Eliminated SST group. Eliminated previously required 8- week PPI trial. Added 4 week PPI washout period. Added 12 week swallowed steroid washout period. Extended duration of treatment to 12 weeks	ESPGHAN guidelines on EoE have recently changed. The diagnosis of PPIREE has been retracted as it is histologically indistinguishable from EoE. Therefore, PPIs are considered a treatment option, not a diagnostic prerequisite. Comparison of two diets and randomization to both groups ensures a comparison of the effects of eliminating additives vs traditional elimination diets, ensures equal allocation to groups, and reduces selection bias. A PPI and steroid washout period is recommended to determine the true severity of the esophagitis.
1,2,8	
v.3
 Removed the additional biopsy	Investigators at our satellite sites expressed slight concern regarding the need to take an additional biopsy. The biopsy was dropped from the protocol as it was intended for future research and was not critical to this study.
5.1	
v.4
 Limited time since diagnostic biopsy	To minimize changes in the eosinophil count since time of biopsy. Eight weeks was allowed because this is a realistic time frame for the next expected visit after the biopsy is taken.
1-4, 6, 8-9	Changed the nature and names of the diets	The feasibility of the diets was of some concern to the team, particularly difficulty recruiting, high drop-out, and

		
the potential for nutritional deficiencies given that formula would not be allowed. Therefore, the study will compare a dairy free diet to dairy free plus additive free diet given that dairy accounts for the majority of allergic reactions. This will make the diets much more acceptable/feasible to the patients/parents and will still answer the question of whether food additives play a role in EoE.

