1 PROTOCOL SUMMARY

1.1 SYNOPSIS

Title:	Food Additive Removal Diet for Pediatric Eosinophilic Esophagitis (FREE)
Study Description:	Prospective, pragmatic standard of care clinical trial comparing dietary therapies of dairy elimination diet (DED) to dairy + food additive elimination diet (FREE) in children with eosinophilic esophagitis.
Objectives:	
Primary Objective: To compare histologic outcomes (eosinophils per high power field: eos/hpf) of dairy elimination diet (DED) to dairy + food additive elimination diet (FREE) in children with eosinophilic esophagitis.
 
Secondary Objective: To compare endoscopic outcomes (Eosinophilic Esophagitis Endoscopic Reference scores: EREFs) of dairy elimination diet (DED) to dairy + food additive elimination diet (FREE) in children with eosinophilic esophagitis
 
Tertiary Objectives: To compare symptomatic (Pediatric Eosinophilic Esophagitis Symptom Severity Module v2.0: PEES) and quality of life (Peds-QL EoE Module 1) outcomes of dairy elimination diet (DED) to dairy + food additive elimination diet (FREE) in children with eosinophilic esophagitis

Endpoints:	
Primary Endpoint: (1) Histologic change differences of maximum eos/hpf baseline vs 12 week endoscopy
 
Secondary Endpoint: (1) EREFs: Eosinophilic Esophagitis Endoscopic Reference Score baseline vs 12 weeks
 
Tertiary Endpoints: (1) Patient Reported Outcomes (Pediatric Eosinophilic Esophagitis Symptom Severity Module (PEES) baseline vs 12 weeks, (2) quality of life (PedsQL-EoE)¹ baseline vs 12 weeks

Study Population:	We will plan to enroll 72 patients. Based on histologic primary outcome efficacy estimates of DED (50%) compared to FREE (estimated 70%) and a sample size of 36 enrolled patients per group (72 total) with 88% power, we will be able to demonstrate a detectable difference of 30% among two

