5.3 STRATEGIES FOR RECRUITMENT AND RETENTION

Providers at participating sites will be educated on the study protocol. Local pathologists will notify study coordinators of patient eligibility. Samples from standard of care biopsies will be batch shipped to the lead site for analysis by the central pathologist. The samples will be identified by the study ID only. Only the originating site can link the codes to the patient.

M. Collin's recommended criteria for the diagnosis of eosinophilic esophagitis (EE) will be used to evaluate the esophageal biopsies.²⁴ The central pathologist, who has extensive experience in the diagnosis of EE will review all biopsies, blind to patient's dietary status. The grading and staging of EE will be based on Collin's criteria, especially to be focused on eosinophilic inflammation, epithelial basal zone changes, eosinophilic abscess, and lamina propria fibrosis. Samples will be returned to the originating sites after central pathology review.

Patients (or in the case of children, the pediatric patient and their parent/legal guardian) will be approached for participation after a clinical assessment has been performed by a GI provider. Study procedures will be performed after obtaining proper consent and/or child assent. In addition, the clinic schedule will be reviewed each week for potential participants. If possible, patients or families will be contacted ahead of time to determine their interest in the study, should they qualify for participation.

Participants will be paid the following: Baseline Visit \$25.00 + 2 weeks of surveys X \$25 + Final Visit \$50.00 = \$125.00 per participant. The telephone follow up and the participant questionnaires must be completed at each designated visit to receive payment. Gift cards will be mailed to participants upon the completion of each eligible visit.

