6.4 CONCOMITANT THERAPY

The following concomitant medications are prohibited during the study:

1. Oral corticosteroids
2. Proton Pump Inhibitors (PPIs)

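### The PPI and swallowed-steroid exclusions in 5.2 are not tied to the date of the baseline biopsy, so some baseline eos/hpf counts may have been taken on drug and the week-12 counts off it

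*Combined protocol and SAP*

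**What the plan says.** The primary endpoint in the synopsis (1.1) is "Histologic change differences of maximum eos/hpf baseline vs 12 week endoscopy". The protocol describes no separate on-study baseline biopsy. Section 5.3 says "Samples from standard of care biopsies will be batch shipped to the lead site for analysis by the central pathologist", and inclusion criterion 6 in 5.1 reads "The biopsy used to diagnose eosinophilic esophagitis was taken no more than 12 weeks prior to the date of enrollment". The diagnostic biopsy therefore serves as the baseline.

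Two exclusions in 5.2 deal with prior drug treatment. For steroids: "The participant has taken prednisone in the last 12 weeks, or has taken fluticasone or budesonide in the last 8 weeks". For PPIs: "The participant is currently taking a PPI (If discontinued, no washout is required". Neither names the date it counts back from; enrollment is the natural reading. Section 6.4 ("The following concomitant medications are prohibited during the study") then lists oral corticosteroids and PPIs.

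Section 6.2 describes a randomization table for each site, with no stratification by prior drug use. Section 9.4 compares the groups by independent-sample t-tests and names no covariate. Medical history and concomitant medications are collected at screening (1.3 and section 8), but no item asks what the child was taking on the day of the biopsy.

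**The concern.** A change score is easiest to read when both measurements are made under the same background treatment. Here the eligibility windows look back from about the time of enrollment, while the baseline count can be as much as 12 weeks older. A child biopsied on a PPI that was stopped the day before enrollment is eligible. So is a child biopsied 10 weeks before enrollment on swallowed budesonide that was stopped soon after. Both are meant to be off drug at week 12. If the drug lowered the baseline count, the recorded improvement is too small by that amount, whichever diet was assigned.

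The Summary of Changes shows that the sponsor had this issue in view. Its v.2 entry gives the reason for a washout: "A PPI and steroid washout period is recommended to determine the true severity of the esophagitis". That washout is superseded and its removal is not an error. The stated reason does explain why treatment at the time of biopsy matters to the count.

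At stake are the precision of the primary comparison, its exposure to chance imbalance in a trial of 72, and any statement about how much children improved on either diet.

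**Working it through.** **1. Dates.** Take enrollment as week 0 and let the biopsy be w weeks earlier, with w at most 12 (5.1).

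| Drug | Look-back in 5.2 | On drug at biopsy possible when | Longest use after biopsy |
|---|---|---|---|
| PPI | current use only | any w | w, so up to 12 weeks |
| Fluticasone/budesonide | 8 weeks | w from 8 to 12 | w − 8, so up to 4 weeks |
| Prednisone | 12 weeks | only w = 12 | 0 weeks |

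The gap is real for PPIs and for the two swallowed steroids. For prednisone it is essentially closed.

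**2. The plan's own power figure.** Section 9.1 gives 50% versus 70%, an SD of 30%, 36 per group and 88% power. It states neither alpha nor sidedness, so I assume 0.05. Treated as a comparison of means, the SE is 30 × √(2/36) = 7.07 and 20/7.07 = 2.83.
- One-sided: Φ(2.83 − 1.645) = 88.2%, which reproduces the stated 88%.
- Two-sided: Φ(2.83 − 1.96) = 80.7% (79.7% by noncentral t).

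I use the two-sided figure as the reference below.

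**3. Illustrative effect on precision.** The documents give neither the share q exposed at biopsy nor the suppression s, so both are assumptions: q = 10-50%, s = 10-30. I also read the 30 and the 20 as eos/hpf, although 9.1 gives them as percentages.

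SD of change = √(30² + q(1 − q)s²)
- Mildest corner (q = 0.1, s = 10): √(900 + 9) = 30.2; two-sided power 80.4% (noncentral t 79.3%).
- Middle (q = 0.25, s = 20): √(900 + 75) = 31.2; power 77.6% (76.4%).
- Worst corner (q = 0.5, s = 30): √(900 + 225) = 33.5; power 71.6% (70.4%).

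**4. Chance imbalance.** The difference between arms in the exposed share has SD √(2q(1 − q)/36), which is 7.1 points at q = 0.1 and 11.8 points at q = 0.5. Multiplied by 1.96 and by s, this could move one trial's difference by 1.96 × 0.071 × 10 = 1.4 up to 1.96 × 0.118 × 30 = 6.9 eos/hpf. This is the same extra variance as in step 3 seen from another side, not a second penalty.

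**5. Within-arm change.** Mean improvement in each arm is understated by q × s: from 0.1 × 10 = 1 to 0.5 × 30 = 15 eos/hpf.

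**6. Bias between arms.** The baseline is fixed before randomization, so its expected value, suppressed or not, is the same in both arms and drops out of the expected difference in change. A simulation with no diet effect, q = 25% and s = 20 gave a mean difference of 0.00 and a two-sided type I error of 5.2%.

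**7. What adjustment does.** I simulated 36 per arm, SD of true change 30, true difference 20, 30% exposed, suppression 25, normal data and equal variance at both times, with 6,000 trials per row. The table gives the SE of the arm difference; all four estimates were unbiased.

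| Baseline/week-12 correlation (assumed) | Change score, exposed baselines | Change score, clean baselines | ANCOVA on recorded baseline | ANCOVA plus exposure indicator |
|---|---|---|---|---|
| 0.2 | 7.5 | 7.0 | 5.6 | 5.6 |
| 0.5 | 7.6 | 7.1 | 6.3 | 6.2 |
| 0.7 | 7.6 | 7.2 | 6.9 | 6.7 |

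Ordinary baseline adjustment more than recovers the loss. The indicator adds a little when the correlation is high.

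**The case against.** The strongest reply is that the trial asks a between-arm question and randomization answers it. A reader might infer from the mixed baselines that FREE versus DED is confounded with drug withdrawal. The documents do not support that: exposure at biopsy precedes randomization and cancels in expectation. This part of the reply stands in full.

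A reader might also infer that some baselines are known to be suppressed. They are not. Every child must have more than 15 eos/hpf at entry. The v.9 log entry says the PPI washout was dropped to admit children who had not responded to a PPI, the group in whom suppression is least expected. This limits the likely size but does not remove the point: a count above 15 shows that the child was not in remission, not that the drug had no effect.

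The steroid part is narrow. The biopsy is the one used for diagnosis, and section 2.2 describes swallowed steroids as treatment for the disease, so many users would have started after it. Steroid use before diagnosis is possible, but nothing shows it is common.

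Finally, screening already collects medical history and concomitant medications, and 10.1.4 provides for medical-record review. It would be wrong to say the plan ignores prior treatment. What is missing is a flag for drug use on the biopsy date and any use of it in the analysis.

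**Conclusion.** The point holds as one of precision and interpretation. Sections 5.1, 5.2 and 6.4 together allow a baseline taken on a PPI, or on fluticasone or budesonide when the biopsy is 8-12 weeks old, to be compared with a week-12 count meant to be off drug. Section 9.4 does nothing about it.

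On the assumed ranges, the SD of change rises from 30 to 30.2-33.5. Two-sided power goes from about 80% to between about 80%, a negligible loss, and about 71%. These figures rest on an assumed alpha of 0.05, on reading percentages as eos/hpf, and on values of q and s that the documents do not give. The true effect could lie at the harmless end.

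It does not follow that the randomized comparison is biased, that every steroid is affected alike, or that adjusting for a partly suppressed baseline is futile; step 7 shows that such adjustment helps. The change is worth making because it is cheap and improves on the unadjusted t-test whether or not many children were exposed.

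**What to change.** - **Record exposure.** Add one CRF field, completed from the chart: on a PPI, or on a swallowed or systemic steroid, at the baseline biopsy (yes/no).
- **Change the primary analysis in 9.4.** Replace the unadjusted t-test for eos/hpf with ANCOVA of the week-12 count on baseline count, arm and the exposure indicator. Baseline adjustment gives most of the gain.
- **Add two supporting analyses.** First, repeat the primary analysis in children off both drug classes at that biopsy. Second, compare the arms at week 12 without using the baseline, as the count or as the proportion below 15 eos/hpf, which section 3 already names as treatment success.
- **State the reference date.** Say in 5.2 which date each look-back counts from, and reconcile it with the biopsy window in 5.1. Which washout applies, if any, is for the sponsor to decide.

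Cost: one CRF field, about one degree of freedom and a little chart review. The analysis in unexposed children will be smaller and less precise, and should be labelled as supportive.

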5.3 STRATEGIES FOR RECRUITMENT AND RETENTION

Providers at participating sites will be educated on the study protocol. Local pathologists will notify study coordinators of patient eligibility. Samples from standard of care biopsies will be batch shipped to the lead site for analysis by the central pathologist. The samples will be identified by the study ID only. Only the originating site can link the codes to the patient.

M. Collin's recommended criteria for the diagnosis of eosinophilic esophagitis (EE) will be used to evaluate the esophageal biopsies.²⁴ The central pathologist, who has extensive experience in the diagnosis of EE will review all biopsies, blind to patient's dietary status. The grading and staging of EE will be based on Collin's criteria, especially to be focused on eosinophilic inflammation, epithelial basal zone changes, eosinophilic abscess, and lamina propria fibrosis. Samples will be returned to the originating sites after central pathology review.

Patients (or in the case of children, the pediatric patient and their parent/legal guardian) will be approached for participation after a clinical assessment has been performed by a GI provider. Study procedures will be performed after obtaining proper consent and/or child assent. In addition, the clinic schedule will be reviewed each week for potential participants. If possible, patients or families will be contacted ahead of time to determine their interest in the study, should they qualify for participation.

Participants will be paid the following: Baseline Visit \$25.00 + 2 weeks of surveys X \$25 + Final Visit \$50.00 = \$125.00 per participant. The telephone follow up and the participant questionnaires must be completed at each designated visit to receive payment. Gift cards will be mailed to participants upon the completion of each eligible visit.

6 STUDY INTERVENTION

6.1 STUDY INTERVENTION(S) ADMINISTRATION

6.1.1 STUDY INTERVENTION DESCRIPTION

Beginning from the date of enrollment/randomization, participation will last 12 weeks (+/- 14 days). Participants will be randomized to DED or FREE study groups. Participants will receive dietary education at the baseline visit.

6.2 MEASURES TO MINIMIZE BIAS: RANDOMIZATION

A randomization table will be generated for each site via *randomization.com* and will be used for assigning eligible participants to a treatment regimen.

To enroll a participant (Visit 1), the investigator (or designee) will assign each participant a 5-digit number which serves as the participant identifier throughout the study.

To randomize a participant (Visit 1), the investigator (or designee) will notify the lead site that a participant has been enrolled. The lead site will randomize the patient.

6.3 STUDY INTERVENTION COMPLIANCE

Study Coordinators will call participants/parents at weeks 2, 3, 5, 6, 8, and 10 to assess difficulty adhering to dietary protocols. If a participant is found to be persistently noncompliant with the diet, the investigator will make a decision as to whether the participant should be withdrawn from the study.

